This will be a 24 week, randomized, double-blind, prospective multi-center trial evaluating the ability of salmeterol to permit a stepwise reduction in inhaled corticosteroids in patients with moderate asthma. All patients with moderate asthma who meet the inclusion and exclusion criteria will receive both a methacholine bronchoprovocation (if baseline FEV₁ ≥ 55% predicted) followed by a sputum induction with hypertonic saline (if post-albuterol FEV₁ > 60% predicted). They will then be treated for a six week run-in period with a uniform dose of ICS (triamcinolone acetonide 400 µg BID) and prn use of the intermediate acting β₂-agonist, albuterol. Beginning with the run-in period, subjects will record in a daily diary their daytime and nighttime symptoms (dyspnea, wheeze, cough, each scored 0-3), AM and PM PEFs, albuterol use, and intercurrent illnesses and hospitalizations. At the end of the run-in period, patients will be randomized within either the SOCS or SLIC protocol based on FEV₁ measurements at the week six visit, and the stability of their PEF measurements during the preceding two weeks. (See diagram, page 24) Patients with greater airflow limitation (FEV₁ ≤ 80% predicted), or greater pulmonary function instability (variability > 20% but FEV₁ > 80% predicted), will be selected for the SLIC protocol. At the end of the six-week run-in period, patients will be randomized in a 2:13 ratio to placebo BID (Group A) and salmeterol 42 µg BID (Group B/C), respectively, for a period of two weeks. At the end of week eight, patients in Group B/C will be classified into subgroup I (FEV₁ > 80% and PEF variability over previous two weeks ≤ 20%) and subgroup II [FEV₁ ≤ 80% predicted or (FEV₁ > 80% predicted and PEF variability over previous two weeks > 20%)]. Then a stratified randomization will take place within each subgroup such that patients in Group B/C will be randomized to Group C (a two step dose reduction/elimination in ICS if they meet safety criteria) (800 – 400 µg at week 8, and 400 – 0 µg at week 16), and Group B (a sham stepwise reduction). All patients in Group A will also undergo a two step dose reduction identical to Group C. After qualifying for SLIC, all patients will receive 2 puffs of salmeterol (42µg) (single blind); one hour later, if their FEV₁ ≥ 55% predicted, methacholine bronchoprovocation will be performed. They will visit the clinical center every 2-4 weeks for an interval history and physical examination, diary review, quality of life measurements, and spirometry (see detailed schematic). At all subsequent visits patients in Groups A, B and C will receive 2 puffs of salmeterol (single blind) and, at designated visits, this will be followed one hour later by methacholine bronchoprovocation if their baseline FEV₁ ≥ 55% predicted. Sputum induction for analysis of markers of inflammation will not be performed at any subsequent visit. Patients will be assigned treatment failure status if their pulmonary function, beta agonist use, or symptom control significantly worsens as defined by a set of strict criteria. If this occurs prior to the scheduled end of the study, the patients may be rescued using a steroid burst algorithm, while at the same time increasing their dose of triamcinolone acetonide to the baseline dose of 800 µg/day. The patients will continue to be followed and all scheduled visits and testing will occur but no further inhaled corticosteroid dose reductions will be attempted. Patients will continue to take their study salmeterol (or placebo) unless the physician can document that treatment failure status was causally related to taking this medication. Glaxo, Inc. has kindly agreed to supply active and placebo canisters for albuterol (Ventolin[®]) and salmeterol xinafoate (Serevent[®]), and Rhône-Poulenc Rorer has graciously consented to supply active and placebo canisters for triamcinolone acetonide (Azmacort[®]) to be used in this protocol.

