2. If patients meet criteria for treatment failure status, their dose of inhaled corticosteroids will be increased to the dose they were receiving at visit 4 (800 $\mu\text{g}/\text{day}$) delivered by an open-label inhaler. Study inhalers of corticosteroids (or its placebo) will be returned to the clinical center. If they meet the criteria detailed in Section VI, they will be treated with appropriate rescue algorithms for an asthma exacerbation. Study inhalers of salmeterol (or placebo) will be continued unless the physician can document that treatment failure status was causally related to taking this medication. They will continue to participate in the study until its termination (intent-to-treat analysis), but no further reductions in inhaled corticosteroid dose will be attempted during this time period. For safety reasons, all subjects will be seen within one week ($\pm 3\text{d}$) from the day they were categorized as achieving treatment failure status. Following this "safety" visit, subsequent protocol visits will continue in accordance with the visit schedule established at Visit 1 (see SOCS/SLIC MOP for details concerning possible replacement of scheduled protocol visits with treatment failure related visits).

IV. OUTCOME VARIABLES

The primary outcome variable will be the time to treatment failure. It will be evaluated using a Kaplan-Meier survival analysis. Secondary outcome indicators will include comparisons of FEV₁, mean peak flow variability (PM-AM peak flow difference normalized by the average of the AM and PM peak flow), methacholine airway responsiveness following premedication with salmeterol (evaluation of bronchoprotective effect), asthma symptom scores, quality of life, and rescue medication use at visits 5-11 to those obtained at visit 4.

Daily data obtained from post-randomization diary cards will be summarized and analyzed as averages. Because subjects are instructed to withhold their study salmeterol (or placebo) for 12 hours prior to a visit, the affected peak flow values will be excluded.

V. PROTOCOL

A. Subjects

1. **Sample size.** This trial has a target sample size of 150 randomized patients, with 20 in Group A, 65 in Group B, and 65 in Group C. See section X.F for the derivation of this sample size.

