A fourth study group on placebo salmeterol and in whom corticosteroids would not be tapered (sham reduction) was not included due to the fact that two previous observations^[7]^[8] failed to demonstrate that even a doubling dose of inhaled corticosteroids was significantly more effective than the introduction of salmeterol therapy. It is also conceivable that the underlying inflammation felt to be important in asthma may increase but remain unrecognized by the patient while they are receiving salmeterol therapy. Although controversial, this adverse effect may be related, at least in part, to reports that chronic use of salmeterol may result in a loss of the initial degree of bronchoprotection from irritant challenges. For this reason, repetitive methacholine challenges will be performed following premedication with salmeterol in an attempt to correlate changes in bronchoprotection over time with clinical outcomes. Both the timing of methacholine challenge testing in relationship to salmeterol dosing and the presence or absence of concomitant corticosteroid treatment may influence the bronchoprotective effect. In patients not receiving inhaled corticosteroids and challenged one hour after salmeterol, a significant loss of the bronchoprotective effect was noted over an 8 week chronic treatment period with salmeterol^[14]. In contrast, when patients (some of whom were receiving inhaled corticosteroids) were challenged 12 hours following chronic salmeterol dosing for the same time interval, no loss of the bronchoprotective effect to methacholine provocation could be demonstrated^[15]. Thus, to maximize the potential of observing an adverse effect of chronic salmeterol therapy on these physiologic measurements, a one hour time interval for evaluation was chosen for this protocol.

H. Anticipated results

It is anticipated that patients randomized to Groups A and B will have treatment failure rates of 50 - 60%^[19] and 5%^[8], respectively, as they approach the end of the randomization period. Since no data are available to calculate comparable values for Group C, a rate which would be considered clinically significant was developed by the ACRN Steering Committee. The committee agreed that a reduction in the treatment failure rate of Group A by more than 50% would be clearly clinically relevant, and the value of 20% was therefore used to calculate the sample size for the various study populations. (see Section X.F for a more detailed discussion)

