Since inhaled corticosteroid therapy will be first reduced and then eliminated in 2 of the 3 study populations, it is anticipated that asthma exacerbations will occur. The protocol contains a number of "safety nets" including frequent visits, phone calls, and well described rescue algorithms so that exacerbation can be recognized early and appropriately treated by both the patient and the ACRN medical support staff. Once an exacerbation requiring oral or parenteral corticosteroid treatment has occurred, the patient will be placed back on their initial dose of inhaled corticosteroid and continued to be followed per the visit schedule designated in the protocol. This event will be recorded as a significant asthma exacerbation rather than an adverse event. Information and data gained as a result of these subsequent visits will be utilized in the "intent to treat" analysis. Should asthma exacerbations become too frequent or too severe following randomization, the ACRN principal investigator may elect to drop the patient from further study participation. Study termination procedures will be completed. Any complication resulting from an asthma exacerbation (pneumothorax, pneumomediastinum, mechanical ventilation, etc.) will be recorded as an adverse event in addition to the documentation also recorded for the significant asthma exacerbation. (See SOCS/SLIC MOP for further details regarding early study termination).

2. Other Medical Complications from Therapy

Complications from chronic salmeterol therapy have been reported to occur in about 12% of patients compared to 23% in patients receiving scheduled albuterol, and 20% of patients only receiving albuterol on a PRN basis^[4].

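### Secondary outcomes at Visits 5-11 include values taken after full-dose inhaled corticosteroid is restored, which favours a finding of no deterioration under Aims 2 and 3

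*Protocol*

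**What the plan says.** **Aims.** Section I and Section II.B (Aims 2 and 3) ask whether ICS can be reduced without deterioration in symptom control, pulmonary function or protection against methacholine.

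**Outcomes.** Section IV makes time to treatment failure primary. The secondary outcomes are FEV1, peak flow variability, methacholine response after salmeterol, and "asthma symptom scores, quality of life, and rescue medication use at visits 5-11 to those obtained at visit 4". The only values that Sections IV and X.E exclude are peak flows affected by withholding study salmeterol before a visit.

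**After failure.** Section III.G.2 says of failed patients that "their dose of inhaled corticosteroids will be increased to the dose they were receiving at visit 4", which is 800 µg/day, open label, and then: "They will continue to participate in the study until its termination (intent-to-treat analysis". Section II.D adds that "all scheduled visits and testing will occur but no further inhaled corticosteroid dose reductions will be attempted". Section VI.B.3 lists prednisone as an option once failure status is reached.

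**Use of the later data.** Section VII.B.1, on exacerbations treated with oral or parenteral corticosteroid, says "Information and data gained as a result of these subsequent visits will be utilized in the" intent-to-treat analysis. Sections II.D and III.G.2 apply the same continued follow-up to every treatment failure.

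**Expected failures.** Section V.H: "It is anticipated that patients randomized to Groups A and B will have treatment failure rates of" 50-60% and 5%. Section X.F uses 60% for A, 5% for B and 20% for C.

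**The concern.** Aims 2 and 3 concern what happens when ICS is withdrawn. A patient in Group C who fails has shown that withdrawal was not tolerated, yet at later visits contributes values obtained on the pre-taper ICS dose, perhaps after prednisone. The more failures an ICS-reduction arm has, the more of its later data are collected on restored treatment. Group B already receives 800 µg/day, so restoration changes the ICS dose only in A and C. The C versus B difference is therefore pulled toward zero, which is the wrong direction of error when the claim is that nothing deteriorated.

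Bronchoprotection is the most exposed outcome. Time to failure does not measure it, so the secondary comparison is the evidence for Aim 3, and Section V.G itself says that concomitant corticosteroid may influence the bronchoprotective effect.

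**Working it through.** No stated figure of the plan is in dispute here. Its failure rates are taken as given.

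**Inputs.** Failure proportions θ: A 0.60 (0.50 at the lower end in Section V.H), B 0.05, C 0.20. Group sizes 20, 65 and 65 (Section V.A). Failure counted after Visit 5, week 8, to week 24, so T = 16 weeks (Section X.E). Hazard −log(1−θ)/T, as in Section X.F. That section assumes exponential times for B and C; applying the same form to A is my assumption.

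**Step 1. Patients past failure at Visit 11**, ignoring withdrawals:
- A: 0.50 to 0.60 × 20 = 10 to 12 patients
- B: 0.05 × 65 = about 3
- C: 0.20 × 65 = 13

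These follow from the planned rates whatever the shape of the hazard.

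**Step 2. Share past failure at week w:** 1 − (1−θ)^((w−8)/16).

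| Week | A (θ = 0.60) | B | C |
|---|---|---|---|
| 12 | 20% | 1% | 5% |
| 16 | 37% | 3% | 11% |
| 20 | 50% | 4% | 15% |
| 24 | 60% | 5% | 20% |

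For week 16, A is 1 − 0.40^0.5 = 0.368 and C is 1 − 0.80^0.5 = 0.106. With θ = 0.50, A is 29% at week 16. Starting the clock at week 6 (T = 18) gives 40% for A (θ = 0.60) and 12% for C. The second reduction takes place at week 16, so constant hazards are only a working assumption and failures may come later than shown.

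**Step 3. Mean scheduled ICS dose at Visit 11**, if all non-failed patients in A and C complete both reductions and all failed patients stay on the restored dose:
- C: 0.20 × 800 = 160 µg/day
- A: 0.50 × 800 = 400 to 0.60 × 800 = 480 µg/day
- B: 800 µg/day

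The intended B−C gap of 800 becomes 640. A and C, intended to be equal, differ by 240 to 320.

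**Step 4. How much deterioration could be hidden.** Let failed patients lose k times what non-failed patients lose if kept on reduced ICS, and let a fraction r of that loss recover once ICS is restored. The share of the arm's mean loss that disappears is θrk / ((1−θ) + θk). Both k and r are assumptions. For C (θ = 0.20):
- k = 1: 10% hidden at r = 0.5, 20% at r = 1
- k = 4: 0.40/1.60 = 25% at r = 0.5, 0.80/1.60 = 50% at r = 1
- r = 0: nothing is hidden
- non-failed patients lose nothing: the hidden share equals r

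For A (θ = 0.60), k = 1 gives 30% at r = 0.5, and k = 4 gives 2.40/2.80 = 86% at r = 1. More is hidden in A than in C for the same k and r, so A versus C narrows if A's loss is at least as large as C's.

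**The case against.** **Failures are already counted.** Time to failure is primary and records the event before ICS is restored, and Section VI.F lists treatment failure and prednisone-defined exacerbations as outcomes. This stands. A reader might infer that a Group C full of failures could be reported as a success; the document does not support that. It does not help bronchoprotection, which no failure criterion measures.

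**Intent-to-treat is legitimate.** Following everyone and analysing as randomized estimates the strategy of step-down with rescue on failure, and question 2 in Section II.C asks about step-down therapy. This also stands, so the all-visit analysis should stay. It answers a different question from the effect of ICS reduction itself, and the protocol does not say which of the two the secondary outcomes address.

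**No single sentence ties post-failure data to each secondary outcome.** True: the link comes from reading Sections II.D, III.G.2, IV and VII.B.1 together. But the protocol positively commits to using the later data and names only one exclusion. An analysis plan, not shown, may add supportive analyses; the point rests on what the protocol fixes.

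**The A versus C control.** A reader might infer that restored ICS destroys this control. It does not: Section X.F powers A versus C on failure, which is untouched, and on secondary outcomes the narrowing works against a salmeterol claim.

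**FEV1 losses in points.** Multiplying failure rates by the 20% in-clinic FEV1 threshold would give 4 points in C and 10-12 in A. Section III.F also allows failure by home peak flow, albuterol use, corticosteroid use, exacerbation or physician judgment, so a 20% fall in every failure, fully recovered, cannot be assumed. Nor could ICS restoration explain any such loss hidden in B, whose ICS dose does not change.

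**Conclusion.** The concern holds for the secondary outcomes that serve Aims 2 and 3. At the planned rates about 20% of Group C and 50-60% of Group A contribute values on restored ICS by Visit 11, and about 11% and 37% at week 16 under constant hazards with 60% for A. The effect of ICS withdrawal is understated in C versus B and in change from Visit 4, which is anti-conservative for a no-deterioration claim. A versus C is narrowed, which is conservative for a salmeterol benefit. The primary outcome is unaffected.

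The direction assumes that restored ICS or prednisone recovers some of the loss. The amount hidden cannot be determined from the document; the 10-50% for C in step 4 only illustrates stated values of k and r.

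**What to change.** In Sections IV and X.E:

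1. Keep the all-visit intent-to-treat analysis and name it as the estimate of the step-down-with-rescue strategy.
2. Pre-specify a co-reported analysis for Aims 2 and 3 in which treatment failure counts as unfavourable, for example a worst-rank comparison of arms at each visit, with patients who failed at or before that visit ranked below all others. Apply it to all secondary outcomes, including methacholine PC20 after salmeterol, which the Section V.F table does not schedule at the treatment failure visit.
3. Require any conclusion of no deterioration in FEV1, peak flow variability, symptoms, quality of life, rescue use or bronchoprotection to be supported by both analyses.

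Do not simply drop post-failure data: the worst patients would leave the comparison, which also favours no deterioration. Do not make a carried-forward failure-visit value the main analysis: it is a single imputation taken at a threshold crossing or acute episode, and may overstate lasting loss.

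Cost: analysis wording and some extra analysis work, with no new visits or tests. The rank analysis partly overlaps with the primary endpoint, so its result should be read with that in mind.

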In order to decrease the likelihood of incorrect drug distribution, each coded package designated for a study participant will have a sheet of removable labels attached to it. When the Clinic Coordinator retrieves a package for the study participant, he/she will remove one of the labels and attach it to the data collection form prior to mailing the form to the DCC. The Clinic Coordinator will initial across the label to indicate that he/she checked to make sure the appropriate package was distributed to the participant.

C. Randomization

When a patient at a particular center is deemed eligible for the study, the Clinic Coordinator will log into the ACRN network server and indicate to the system that a patient requires randomization. After entering the pertinent information, the Clinic Coordinator will be asked to verify that all of the information has been reviewed carefully and the patient is eligible. If so, the Clinic Coordinator will be given a packet number, from which all medication for that patient will be dispensed. In order to maintain security of the randomization schedules, the data manager of the DCC will automatically receive a notice from the ACRN network server that a patient has been randomized. If no follow-up information is forthcoming on such a patient, the data manager will contact the Clinic Coordinators concerning the status of the patient.

As described in Section IID, this protocol requires randomization of patients on two occasions. Patients at Visit 4 are randomized to either active salmeterol (13/15) or placebo salmeterol (2/15). Patients on active salmeterol at Visit 5 are randomized to receive the ICS reduction (Group C) or the sham ICS reduction (Group B), whereas the placebo salmeterol patients (Group A) will undergo the ICS reduction.

D. Stratification

The randomization scheme will be stratified according to center because differences among clinical centers typically yield a large amount of variability. In addition, each Clinical Center will be restricted to enroll no more than 25% of its target sample size of patients to be between the ages of 12 and 18.

Within subgroup I and subgroup II (see Section IID for definitions) of each clinical center an adaptive randomization scheme at Visit 5 will be invoked in order to balance the treatment arms with respect to the following strata:

ethnic group (white, black, Hispanic, native American, Asian, Other)
gender (male, female)
age (adolescent, adult)

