The strata of a particular patient are noted and the marginal frequencies of these strata are summed for each treatment arm. Then the patient is assigned to that treatment arm which has the smallest sum of marginal frequencies^[16].

E. Statistical Analysis

The primary response variables in this study are time and occurrence of treatment failure after visit 5, where treatment failure is defined in Section III. Kaplan-Meier survival curves will be constructed for the three treatment arms. Statistical tests, such as the logrank test and the generalized Wilcoxon test, will be applied to compare the survival curves of the groups.

In addition, a proportional hazards regression analysis will be applied, which allows for comparing the survival curves of the groups in the presence of other covariates. In this type of analysis the hazard function at time t is modelled as

$$h(t; \mathbf{x}) = h_0(t)\exp(\mathbf{x}^T\xi)$$

where

$h_0(t)$ is the unspecified baseline hazard,

$\mathbf{x} = [x_1 \dots x_k]^T$ is a vector of explanatory variables, and

$\xi = [\xi_1 \dots \xi_k]^T$ is a vector of unknown parameters.

The vector \mathbf{x} will include indicator variables for treatment assignment, Clinical Center, and treatment \times center interactions. The assumption of proportional hazards is important for the logrank test and the proportional hazards regression. This will be assessed via graphical procedures (comparing log survival plots) and statistical tests (including time-dependent covariates in the proportional hazards regression and testing for significance).

Safety of methacholine challenge will be examined by analyzing the frequency of adverse events following clinic visits at which methacholine challenge is performed, compared with the frequency following visits at which it is not. McNemar's test will be applied for this purpose because of the correlated responses within each subject. The efficacy of methacholine challenge will be analyzed by correlating PC_{20} with other measures of asthma outcome, such as AM and PM PEF, FEV_1 , symptom scores, rescue beta-agonist use, and quality of life scores. Correlation coefficient estimates and confidence intervals, specifically designed for longitudinal data, will be calculated for this purpose. Daily data obtained from post-randomization diary cards will be summarized and analyzed as

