averages. Because subjects are instructed to withhold their study salmeterol (or placebo) for 12 hours prior to a visit, the appropriate peak flow values prior to the visit will be excluded.

F. Sample Size Calculation

The primary comparison of interest in this trial is testing whether the time-to-failure responses for Groups B and C are significantly different. Schoenfeld^[17] described a formula for sample size calculations based on a proportional hazards regression for a time-to-failure response. For a one-sided test in a two-arm trial, the total number of failures required is

$$4(z_{1-\beta} + z_{1-\alpha})^2 / \{\log(\Delta)\}^2$$

where

z_γ represents the 100 γ percentile from the standard normal distribution,

α is the Type I error rate,

β is the Type II error rate,

p_1 is the proportion randomized to treatment arm #1 (Group C),

p_2 is the proportion randomized to treatment arm #2 (Group B in the primary case and Group A in the secondary case), and

Δ is the hazard ratio of the two treatment arms.

If exponential distributions are assumed for Groups B and C, then the corresponding hazard functions and their ratio is constant and not a function of time. Letting θ_1 and θ_2 denote the proportion of failures in treatment arm #1 and #2, respectively, and letting T denote the length of the trial, then the hazard functions are $-\log(1-\theta_1)/T$ and $-\log(1-\theta_2)/T$, respectively, and the hazard ratio is $\Delta = \log(1-\theta_1)/\log(1-\theta_2)$.

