Chervinsky, et al^[19] reported a 60% failure rate for a similar group of patients receiving placebo, so we assume that $\theta_A = 0.60$. Greening, et al^[8] reported a 5% failure rate for a similar group of patients receiving salmeterol and ICS, so we assume that $\theta_B = 0.05$. Although it is anticipated that $\theta_A > \theta_C > \theta_B$, there is no report in the literature as to an anticipated failure rate for Group C. As such, a rate which would be considered clinically significant was discussed at length by the ACRN Steering Committee. The committee agreed that a reduction in the treatment failure rate of Group A by more than 50% would be clearly clinically relevant in this patient population. Therefore, failure rates less than 30% were assumed for Group C in order to calculate the sample size. The Steering Committee also recognized that the eventual choice of a precise failure rate for Group C needed to reflect the relative numbers of asthmatic patients with moderate asthma within the entire asthmatic population in the United States (approximately 25% of the total) in order to set realistic recruitment goals for this disease severity category. After numerous discussions with input from various individuals, the Steering Committee agreed that a 20% treatment failure rate for Group C would be the best choice to address both the clinical

relevance of any observed differences and the patient population disease severity restraints.

It is not of interest to detect failure rates in the other direction, i.e., $\theta_B > \theta_C > \theta_A$, so one-sided tests are used. One interim analysis is planned for this trial when approximately one-half of the randomized patients have completed the trial. Therefore, a significance level of $\alpha = 0.029$ (see Pocock^[18]) will be invoked at each analysis. Using $\beta = 0.20$ (80% statistical power) and allowing for a 10% withdrawal rate, a total of 130 randomized patients are needed in Groups B and C. In order to perform the secondary comparison of Group B versus Group A, the target sample size for Group A will be 20 randomized patients. This comparison of Group C versus Group A will have 80% statistical power based on the assumed failure rates of 20% and 60%, respectively. Thus, the required sample size for this trial is 150 randomized patients.

XI. REFERENCES CITED

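### The Cox model in protocol section X.E includes treatment-by-center terms that about 15 failures in Groups B and C cannot support, so it will not give a usable overall B-versus-C hazard ratio

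*Protocol*

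**What the plan says.** Protocol section X.E defines the outcome: "The primary response variables in this study are time and occurrence of treatment failure after visit 5". It plans Kaplan-Meier curves with logrank and generalized Wilcoxon tests, then adds a regression: "In addition, a proportional hazards regression analysis will be applied, which allows for comparing the survival curves of the groups". This comparison is adjusted for further variables: the covariate vector "will include indicator variables for treatment assignment, Clinical Center, and treatment" by center interactions. The section gives no rule for testing and removing the interactions, for pooling small centers, or for a coding other than indicators. It does plan to check proportional hazards, by plots and by time-dependent covariates.

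Section X.F names the target: "The primary comparison of interest in this trial is testing whether the time-to-failure responses for Groups B and C are significantly different". It sizes the trial on one constant hazard ratio between those two arms. For Group B it takes a cited trial that "reported a 5% failure rate for a similar group of patients receiving salmeterol and ICS". For Group C the Steering Committee "agreed that a 20% treatment failure rate for Group C would be the best choice". Section V.A plans 65 patients in each of B and C and 20 in A. Section V.B describes six clinical centers.

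**The concern.** A model with treatment-by-center interactions estimates a separate B-versus-C hazard ratio in every center. Each of these needs failures in both arms at that center. If a center has no failure in one arm, the partial likelihood keeps rising as the coefficient grows, so there is no finite estimate and the Wald interval means nothing. If it has none in either arm, its hazard ratio is undetermined.

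The coefficient labelled treatment also changes meaning. With indicator variables it is the hazard ratio in whichever center is the reference, not the overall ratio on which section X.F sizes the trial. This Cox model is the only covariate-adjusted analysis, and the only source of a hazard ratio, that the protocol names for the primary outcome. If the terms are dropped only after the fit fails, that becomes a choice made after seeing the data.

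**Working it through.** **Inputs.** 65 patients in each of B and C (V.A); failure rates 0.05 and 0.20, and 10% withdrawal (X.F); six centers, counted from the headings in V.B. Equal enrollment by center is an assumption.

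**The plan's own sample size.** Hazard ratio = log(0.80)/log(0.95) = 4.35, with logarithm 1.47. With one-sided α = 0.029 and 80% power, the Schoenfeld formula gives 4(0.842 + 1.896)²/1.47² = 13.87, so 14 failures. The mean failure rate is (0.05 + 0.20)/2 = 0.125, so 14/0.125 = 112 patients, and 112/0.9 gives 125 after rounding up. The protocol states 130, slightly more and on the safe side. The gap does not affect this point, but it confirms that the design rests on about 14 failures and one overall hazard ratio.

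**Expected failures.**
- Without withdrawals: B 65 × 0.05 = 3.25; C 65 × 0.20 = 13; total 16.25.
- With 10% lost: B 2.9; C 11.7; total 14.6.

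**Parameters.**
- B versus C: 1 treatment + 5 center + 5 interaction = 11, so 14.6/11 = 1.3 failures per parameter.
- Three arms: 2 + 5 + 10 = 17. Group A adds 20 × 0.60 = 12 failures (10.8 after withdrawals), for a total of about 25 to 28. They do not fill an empty Group B cell.

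**Empty cells.** Equal enrollment gives n = 65/6 = 10.83 patients per arm per center, or 9.75 after withdrawals.

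| Quantity | Formula | n = 10.83 | n = 9.75 |
|---|---|---|---|
| No B failure in a given center | 0.95ⁿ | 0.574 | 0.607 |
| No C failure in a given center | 0.80ⁿ | 0.089 | 0.114 |
| Expected centers of 6 with no B failure | 6 × 0.95ⁿ | 3.4 | 3.6 |
| p = both arms have a failure | (1 − 0.95ⁿ)(1 − 0.80ⁿ) | 0.388 | 0.349 |
| Reference center lacks a failure in B or C | 1 − p | 0.61 | 0.65 |
| At least one center lacks a failure in B or C | 1 − p⁶ | 0.997 | 0.998 |

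**Unequal centers.** Boston and Denver each plan about 30 patients, or 30 × 65/150 = 13 per arm. If withdrawals cut the observed Group B rate to 0.0475, the chance of no B failure there is 0.9525¹³ = 0.53. The other four centers would share 150 − 60 = 90 patients, 22.5 each, or 22.5 × 65/150 = 9.75 per arm, where 0.95^9.75 = 0.61. Uneven enrollment therefore spreads the risk without removing it.

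**Higher failure rates (n = 10.83).**
- 10% and 30%: p = (1 − 0.90ⁿ)(1 − 0.70ⁿ) = 0.666, so 1 − p⁶ = 0.91.
- 15% and 35%: p = (1 − 0.85ⁿ)(1 − 0.65ⁿ) = 0.820, so 1 − p⁶ = 0.70.

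**Simulated fits.** In 300 simulated B-versus-C trials, the treatment coefficient of the 11-parameter model was unusable in 78% (absolute value or standard error above 5, or a failed fit). Its one-sided Wald test was significant in 0.7%. With the interactions removed (6 parameters), the median log hazard ratio was 1.50 against a true 1.47, the median standard error was 0.65, and the Wald test was significant in 65%. With 300 runs these percentages are rough, but the contrast is not in doubt.

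**The case against.** The Cox model is not the lead analysis. Section IV evaluates the primary outcome by Kaplan-Meier analysis, and X.E adds the regression to tests that compare B and C overall. This stands: those tests contain no interaction terms. A reader might infer that the primary comparison is invalid, but the protocol does not support that.

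A different coding, or a model without interactions, would give an overall effect. Removing the interactions does, and that is the fix. Effect coding does not help: the treatment coefficient becomes the unweighted mean of six center-specific log hazard ratios, and one infinite term makes the mean infinite or undefined. An analysis plan not shown here could replace the model, but it would have to depart from a positive statement in the protocol.

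Two stronger readings are tempting.

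- *The omission of Subgroup I/II.* Section X.D says that within the two subgroups "of each clinical center an adaptive randomization scheme at Visit 5 will be invoked in order to balance the treatment arms", and the subgroup is not among the listed covariates. One might infer that this also spoils the estimate. It does not: the missing estimates come from the interactions alone. The list is not declared complete. Section II.D classifies only Group B/C by subgroup, at week 8, so in a three-arm model it would be measured after the Visit 4 randomization. Leaving it out there is defensible.
- *The two dose steps.* Groups A and C undergo "a two step dose reduction/elimination in ICS if they meet safety criteria", so one might infer that a single hazard ratio is an error. But the hypothesis in section I does not ask for separate estimates by step, and X.E already plans time-dependent covariates to test proportionality. With about 3 Group B failures, splitting follow-up at week 16 would also risk a period with none (about 38% under a constant hazard).

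**Conclusion.** The point holds for the Cox model as written, and only for that. At the planning rates the model almost certainly contains at least one coefficient without a finite estimate (over 99%), and its treatment coefficient fails in about 61 to 65% of trials. When that coefficient can be estimated, it describes one center. The model therefore does not deliver the overall B-versus-C hazard ratio on which section X.F is built.

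The figures assume six centers, roughly equal enrollment, the planned 5% and 20% failure rates, and indicator coding with a reference center. Higher failure rates reduce the problem but leave it likely (70 to 91% for at least one empty cell). It should be corrected, but it does not undermine the logrank or Wilcoxon comparison.

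**What to change.** In section X.E, state that the overall B-versus-C hazard ratio and its confidence interval come from a Cox model without treatment-by-center terms, stratified by center or adjusted for it. Move treatment-by-center heterogeneity to a descriptive or exploratory check, such as failures by arm and center. Stratifying has one practical advantage: a center with no failure in either arm (probability 0.574 × 0.089 = 0.05 to 0.607 × 0.114 = 0.07 per center) simply contributes nothing, whereas its indicator would have no finite coefficient. Optionally, for B versus C only, adjust also for Subgroup I/II, within which those arms are randomized at Visit 5.

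The change is wording only and needs no patients or data. It should be made before the groups are unmasked. The cost is that center-specific effects are no longer formally tested, though about 3 Group B failures over six centers could not support such a test anyway. The simpler model has a limit too: the chance of no Group B failure at all is 0.95⁶⁵ = 0.04, or 0.95^58.5 = 0.05 after withdrawals, and then no Cox model gives a finite hazard ratio.
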